# **Hematologic Toxicity:**

- Anemia is an expected toxicity of Hu5F9-G4 (magrolimab) and dinutuximab, especially in patients who have had extensive prior therapy with chemotherapy, and therefore anemia and a need for blood transfusions will not be considered a DLT. Grade 3 hemolytic anemia that is medically significant, requires hospitalization or prolongation of existing hospitalization, is disabling, or limits self-care activities of daily life (ADLs) will be considered a DLT.
- Thrombocytopenia can be expected in this heavily pretreated population who have had extensive prior therapy with chemotherapy, and therefore platelet count decreased in the absence of hemorrhage will not be considered a DLT unless < 25,000/mcL for > 14 days despite supportive care.
- Grade 3 or 4 lymphopenia or leukopenia not associated with other clinically significant consequences.

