### 6.1.1.1 Safety Assessment During "single agent Safety Lead-In"

Patients aged ≥2 or < 18 years of age will be enrolled on the "single agent Safety Lead-In", and will receive a therapeutic dose of Hu5F9-G4 (magrolimab) (30 mg/kg IV) on Day 1 of weeks 2 and 3 for a 21-day "single agent Safety Lead-In" cycle (see **Figure 1** and **Figure 2**). An assessment for DLTs as defined in **Section 6.3** will be performed during and at the end of the 21-day "single agent Safety Lead-In".

Any patient who does not develop DLT during the "single agent Safety Lead-In" may proceed to Cycle 1 (combination therapy with Hu5F9-G4 (magrolimab) plus dinutuximab) and will be evaluable for safety assessment during and after Cycle 1. When dinutuximab is administered immediately after Hu5F9-G4 (magrolimab), redosing with acetaminophen and diphenhydramine is not necessary. The intravenous line should be flushed well between drug administrations.

Patient enrollment and start of treatment during the safety "single agent Safety Lead-In" assessment will be staggered by 7 days for each patient enrolled. Three patients will initially be enrolled at Dose Level 1 (30 mg/kg IV).

- If 0 of the initial 3 patients develops a DLT during the 21-day "single agent Safety Lead-In", the next phase of safety will be evaluated in Cycle 1 as outlined below (Section 6.1.1.2).
- If 1 of the initial 3 patients develops a DLT (Section 6.3) during the 21-day "single agent Safety Lead-In", then an additional 3 patients will be enrolled at Dose Level 1.
  - o If 0 of these 3 additional patients (totaling 1/6) develops a DLT during the 21-day "single agent Safety Lead-In", the study will continue to evaluate DLTs in Cycle 1 as outlined below (Section 6.1.1.2).
  - o If ≥1 of these 3 additional patients (totaling 2/6) develop a DLT, the dose of Hu5F9-G4 (magrolimab) will be de-escalated to Dose Level -1 (20 mg/kg) during weeks 2 and 3 in the next 3 patients. The safety of Dose Level -1 will be similarly evaluated in 3-6 patients.
- If ≥ 2 of the initial 3 patients develop a DLT during the 21-day "single agent Safety Lead-In", the dose of Hu5F9-G4 (magrolimab) will be de-escalated to Dose Level -1 (20 mg/kg) during weeks 2 and 3, in the next 3 patients. The safety of Dose Level -1 will be similarly evaluated in 3-6 patients.
- If ≥ 2 patients develop DLT during the "single agent Safety Lead-In" using Dose Level -1, enrollment will pause pending discussions with the sponsor, IRB and FDA.

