# 6.3 Definition of Dose-Limiting Toxicity

Adverse events that occur within the first 21 days of the 'single agent Lead-In' dosing of Hu5F9-G4 (magrolimab) or during the 21 days of Cycle 1 during the combination Hu5F9-G4 (magrolimab) and dinutuximab drug infusions, are *at least possibly related* to at least 1 study agent, and are  $\geq$  *Grade 3 in severity* will be considered DLTs with the following additional criteria or exceptions:

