#### Non-hematological Toxicity:

- Any Grade 3 or greater, non-hematological toxicity will be considered a DLT with the following *exceptions*:
  - a. Pain and sensory neuropathy are expected toxicities of dinutuximab, but pain or sensory neuropathy at levels described in Table 8: Adverse Reactions Requiring Permanent Discontinuation of Dinutuximab will be considered a DLT. Pain requiring sedation and respiratory support for control will also be considered a DLT.
  - b. Tumor lysis syndrome, including associated abnormalities (e.g., electrolytes, uric acid, renal function).
  - c. Grade 3 low electrolyte levels that are correctable and asymptomatic.
  - d. Grade 3 hypoalbuminemia. Such individuals should receive supplementation as indicated. Hypocalcemia toxicity grade should be assigned based on the calcium level corrected for degree of hypoalbuminemia according to the following formula: for every albumin decrease of 1 gm/dL a total calcium increase of 0.2 mmol/L is to be made.
  - e. Grade 3 transaminase, alkaline phosphatase, bilirubin or other liver function test elevation, provided there is resolution to  $\leq$  grade 2 with supportive care within 7 days and is not associated with other clinically

significant consequences. Grade 3 transaminase elevation, alkaline phosphatase or hyperbilirubinemia elevation of any duration in patients with liver involvement due to tumor will not be considered a DLT, although Grade 4 hepatic toxicity will be considered DLT.

- f. Transient Grade 3 nausea, vomiting, diarrhea, local reactions, influenza-like symptoms, myalgias, fever, headache, acute pain, or skin toxicity that resolves to ≤Grade 2 within ≤72 hours after medical management (e.g., supportive care, including immunosuppressant treatment) has been initiated.
- g. Grade 3 fatigue that resolves to ≤Grade 2 within 1 week.
- h. Grade 3 infusion reactions in the absence of an optimal pretreatment regimen, which is defined as acetaminophen or a comparable non-steroidal anti-inflammatory agent, plus an antihistamine and corticosteroids.
- i. Grade 3 or 4 infection or neutropenic fever although Grade 4 infection uncontrolled for > 7 days will be considered DLT.
- j. Grade 3 electrolyte disturbances (hyperkalemia, hypophosphatemia, hyperuricemia, etc.) that resolves to ≤Grade 2 or baseline within 1 week. Grade 4 hyponatremia not responsive to appropriate fluid management for dinutuximab will be considered a DLT.

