# 9.2 Study Design/Endpoints

# **9.2.1** Dose Finding Cohort (Arm A) Primary Endpoint

The primary objective is to determine the safety and tolerability of Hu5F9-G4 (magrolimab) in combination with dinutuximab in children and young adults with relapsed/refractory (R/R) neuroblastoma (NBL) and osteosarcoma, and to determine the recommended phase 2 dose (RP2D) of Hu5F9-G4 (magrolimab) given in combination with dinutuximab. All patients who receive any amount of the study drug will be evaluable for toxicity. There will be two timepoints at which dose limiting toxicities (DLTs) will be measured to establish the maximum tolerated dose (MTD): during the 'single agent Safety Lead-In' in which patients with osteosarcoma or NBL will receive Hu5F9-G4 (magrolimab) during the first 3 weeks, and during Cycle 1 (21 days) of the combination of Hu5F9-G4 (magrolimab) and dinutuximab (Figure 2) as described in Section 6.3. If patients in the 'single agent Safety Lead-in' cohort or during Cycle 1 combination of Hu5F9-G4 (magrolimab) and dinutuximab discontinue participation prior to the safety evaluation for reasons other than the occurrence of a DLT (e.g., withdrawal of consent, rapid tumor progression, death due to rapid tumor progression, AE that does not meet DLT criteria), they will not be evaluable for MTD and will be replaced in the appropriate dose-finding group ('single agent Safety Lead-In' or Cycle 1 of Arm A).

If a patient is replaced to determine safety in Cycle 1 of Arm A, and the dose of Hu5F9-G4 (magrolimab) has NOT been deemed safe, i.e., 3 patients have not completed the Safety Lead-in without DLT, the replaced patient will undergo priming dose of Hu5F9-G4 (magrolimab), undergo the Safety Lead-in and then proceed to Cycle 1. This patient will be evaluable for DLT in the Safety Lead-in group.

If 3 patients have received Hu5F9-G4 (magrolimab) during the Safety Lead-in and the dose of Hu5F9-G4 (magrolimab) has been deemed safe, a patient being replaced in Cycle 1 of Arm A, will undergo a priming dose of Hu5F9-G4 (magrolimab) and proceed directly to Cycle 1 (combination of Hu5F9-G4 (magrolimab) and dinutuximab) for determination of MTD in the combination cohort.

Establishment of safety of the combination of Hu5F9-G4 (magrolimab) and dinutuximab will be completed in the first 3 patients enrolled in Arm B as described in section 6.1.1.2.

The safety and tolerability of Hu5F9-G4 (magrolimab) plus dinutuximab will be assessed by:

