# **10.1.1** CAEPRs for CTEP IND Agent(s)

#### 10.1.1.1 CAEPRs for Hu5F9-G4 (magrolimab), NSC 809249

Below is the CAEPR for Hu5F9-G4 (magrolimab). Frequency is based on 1328 patients.

Version 2.2, December 6, 2023 **Adverse Events with Possible** Relationship to Hu5F9-G4 (Magrolimab) **Specific Protocol Exceptions to** (CTCAE 5.0 Term) Expedited Reporting (SPEER) [n=1328]Likely (>20%) Less Likely (<=20%) Rare but Serious (<3%) BLOOD AND LYMPHATIC SYSTEM DISORDERS Anemia (Gr 2) Anemia Blood and lymphatic system disorders - Other (red blood cell agglutination) Febrile neutropenia Febrile neutropenia (Gr 2) Hemolysis GASTROINTESTINAL DISORDERS Abdominal pain (Gr 2) Abdominal pain Diarrhea Diarrhea (Gr 2) Nausea (Gr 2) Nausea Vomiting Vomiting (Gr 2) GENERAL DISORDERS AND ADMINISTRATION SITE CONDITIONS Chills (Gr 2) Chills Fatigue Fatigue (Gr 2) Fever Fever (Gr 2) Generalized edema INFECTIONS AND INFESTATIONS Lung infection Sepsis INJURY, POISONING AND PROCEDURAL COMPLICATIONS Infusion related reaction Infusion related reaction (Gr 2) INVESTIGATIONS Blood bilirubin increased Blood bilirubin increased (Gr 2) Lymphocyte count decreased Lymphocyte count decreased (Gr 2) Neutrophil count decreased Neutrophil count decreased (Gr 2) Platelet count decreased Platelet count decreased (Gr 2) White blood cell decreased White blood cell decreased (Gr 2) METABOLISM AND NUTRITION DISORDERS Anorexia (Gr 2) Anorexia Hypokalemia Hypokalemia (Gr 2) MUSCULOSKELETAL AND CONNECTIVE TISSUE DISORDERS Arthralgia Back pain NERVOUS SYSTEM DISORDERS Dizziness Headache (Gr 2) Headache RESPIRATORY, THORACIC AND MEDIASTINAL DISORDERS

Rel	Specific Protocol Exceptions to Expedited Reporting (SPEER)		
Likely (>20%)	Less Likely (<=20%)	Rare but Serious (<3%)	
	Cough		
	Dyspnea		
SKIN AND SUBCUTANEOU	S TISSUE DISORDERS		
VASCULAR DISORDERS			
Hypotension			

This table will be updated as the toxicity profile of the agent is revised. Updates will be distributed to all Principal Investigators at the time of revision. The current version can be obtained by contacting [contact]. Your name, the name of the investigator, the protocol and the agent should be included in the e-mail.

Adverse events reported on Hu5F9-G4 (Magrolimab) trials, but for which there is insufficient evidence to suggest that there was a reasonable possibility that Hu5F9-G4 (Magrolimab) caused the adverse event:

BLOOD AND LYMPHATIC SYSTEM DISORDERS - Thrombotic thrombocytopenic purpura

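### Section 6.3 exempts anemia from the DLT definition without a grade limit and restores only Grade 3 hemolytic anemia, so Grade 4-5 hemolytic anemia can be read as not counting

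*Combined protocol and SAP*

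**What the plan says.** Section 6.3 starts from a general rule: events in the DLT window that are at least possibly related and Grade 3 or higher "will be considered DLTs with the following additional criteria or exceptions".

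The first hematologic bullet describes anemia as expected in this population, "therefore anemia and a need for blood transfusions will not be considered a DLT". No grade is attached. The next sentence of that bullet makes one kind of anemia a DLT: "Grade 3 hemolytic anemia that is medically significant, requires hospitalization or prolongation of existing hospitalization, is disabling, or limits self-care" activities. Grades 4 and 5 are not mentioned.

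Three other places bear on the point:

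- Section 7.1, in the table headed Anemia, has a row for Grade 3 hemolytic anemia. Its Grade 4 row stops magrolimab permanently at first occurrence unless the patient is benefitting clinically. It does not say whether the event is a DLT.
- Section 9.2.1 deals with Arm A patients who leave before the safety evaluation for reasons other than a DLT. One listed reason is an "AE that does not meet DLT criteria), they will not be evaluable for MTD and will be replaced".
- Section 10.1.1.1 lists Anemia and Hemolysis as separate risk terms for magrolimab. Hemolysis is in the rare-but-serious category, below 3%, from 1328 patients.

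**The concern.** The hemolytic sentence sits inside the anemia bullet and works as an exception to the exemption. Taken at its word, a qualifying Grade 3 hemolytic anemia is a DLT, while a life-threatening or fatal one stays within exempt anemia. That ordering cannot be what a safety rule wants.

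The DLT count decides de-escalation and the RP2D from cohorts of three to six patients. It also feeds the DLT check on the first three Arm B patients (Section 6.1.1.2) and the continued DLT monitoring in the expansion cohorts (Section 6.4). Section 7.2.4 says that magrolimab binds red cells and leads to their phagocytosis, so severe red-cell destruction is a foreseeable toxicity of this drug and should not need interpretation when it occurs.

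The individual patient is largely protected by the Grade 4 anemia rule in Section 7.1. The gap is in the cohort decision: a patient stopped under that rule before the safety evaluation could be treated as non-evaluable under Section 9.2.1 and replaced, so the event would leave both numerator and denominator.

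**Working it through.** The plan gives no figure to reproduce, so the check is first textual and then a calculation of size.

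**Reading the text.** Two readings are open.

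1. *Hemolytic anemia is a kind of anemia.* It is then exempt at every grade, and only the named Grade 3 events return. The placement in one bullet supports this, as does Section 7.1, which puts hemolytic anemia under Anemia.
2. *Hemolytic anemia is a separate event.* The exemption does not reach it, and the general Grade 3-or-higher rule still counts Grades 4 and 5. The separate Hemolysis term in Section 10.1.1.1 supports this.

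Elsewhere Section 6.3 gives the grade range when it defines what counts. The non-hematologic rule reads "Any Grade 3 or greater, non-hematological toxicity will be considered a DLT", and the liver exception adds "although Grade 4 hepatic toxicity will be considered DLT". Items i and j likewise name the Grade 4 infection and Grade 4 hyponatremia that count. The anemia bullet has no such wording.

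**Effect once an event has occurred.** Under Sections 6.1.1.1 and 6.1.1.2, 0/3 or 1/6 passes and two or more DLTs lead to de-escalation; the lead-in text for the second three patients is "totaling 2/6) develop a DLT, the dose of Hu5F9-G4 (magrolimab) will be de-escalated to Dose Level -1". If one event is not counted:

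- 2/6 becomes 1/6, and de-escalation does not happen.
- 1/3 becomes 0/3, and the second three patients at that dose are not enrolled. Those three would have triggered de-escalation with probability 1 − (1 − p)³: 1 − 0.9³ = 0.271 at p = 10%, and 1 − 0.8³ = 0.488 at p = 20%.

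**Average effect.** Let o be the rate of other DLTs and h the rate of Grade 4-5 hemolytic anemia, taken as independent. With q = 1 − p, the chance that a dose level passes one 3+3 check is

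P(pass) = q³ + 3pq² × q³,

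with p = o if the event is not counted and p = 1 − (1 − o)(1 − h) if it is.

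The documents give neither rate. I assume o = 0%, 10% and 20%, and h = 1% and 3%. The 3% is the ceiling of the all-grade Hemolysis category, so the Grade 4-5 rate in that database should be lower; the database is not this pediatric combination.

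Worked case, o = 10%, h = 3%:

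- Not counted: 0.9³ + 3(0.1)(0.9²)(0.9³) = 0.7290 + 0.1771 = 0.9061.
- Counted: p = 1 − 0.90 × 0.97 = 0.127, q = 0.873, giving 0.6653 + 0.1932 = 0.8585.

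| h | o | Not counted | Counted | Difference (points) |
|---|---|---|---|---|
| 3% | 0% | 1.0000 | 0.9900 | 1.0 |
| 3% | 10% | 0.9061 | 0.8585 | 4.8 |
| 3% | 20% | 0.7086 | 0.6564 | 5.2 |
| 1% | 0% | 1.0000 | 0.9988 | 0.1 |
| 1% | 10% | 0.9061 | 0.8910 | 1.5 |
| 1% | 20% | 0.7086 | 0.6912 | 1.7 |

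The not-counted column keeps the affected patient in the denominator. If the patient is replaced instead, the DLT rate among evaluable patients is o / (1 − h(1 − o)) = 0.10 / 0.973 = 0.1028 in the worked case, and the pass probability is 0.902 rather than 0.906. The picture does not change.

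**The case against.** The best answer is that the general rule already covers the event. The exemption rests on anemia being expected after heavy prior chemotherapy and on transfusion need, which does not describe life-threatening hemolysis. On this view the next sentence only narrows which Grade 3 hemolytic events count and leaves higher grades to the default. The documents also separate the two conditions elsewhere: Section 3.2.8 excludes recent hemolytic anemia apart from the transfusion-dependence criterion in 3.2.6, and Section 10.1.1.1 has separate terms. Several non-hematologic exceptions in Section 6.3 (items c, d, f, g, h) mention only Grade 3 without saying that Grade 4 counts. Finally, Section 13.1.2 has the study chair enter DLT evaluations that are reviewed weekly, and deaths need expedited reporting under Section 10.3.3, so a severe event would be seen.

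Most of this stands as evidence of intent, and I accept that Grade 4-5 events were probably meant to count. It does not settle the text. The listed non-hematologic items are exemptions capped at Grade 3, so Grade 4 falls back to the default; the anemia exemption has no cap, so the default may not be reached. The weekly review applies the Section 6.3 definition and so inherits its ambiguity. Classification would then be decided after the event is known, which a prespecified dose-finding rule is meant to avoid. The objection that the average effect is small is correct.

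**Conclusion.** The concern holds as a defect of wording in a safety rule. Section 6.3 can be read to leave Grade 4-5 hemolytic anemia out of the DLT count, and nothing else in the protocol rules that reading out. It is not shown that the sponsor intends the exclusion.

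An event left out can change a dose decision outright. Averaged over the chance that one occurs, the effect on passing a single 3+3 check runs from 0.1 to 5.2 percentage points over the assumed rates, and the upper end uses an all-grade ceiling for a Grade 4-5 rate. The case for a change rests on the consequence when the event happens and on the ease of the correction, not on frequency. I would make the change, with medium confidence that the gap would ever affect a decision.

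**What to change.** In the first hematologic bullet of Section 6.3, after the existing Grade 3 qualifiers, add: *or any Grade 4 or 5 hemolytic anemia*. Then state that the anemia exemption does not apply to hemolytic anemia. Changing the opening to *Grade 3 or greater* would also name the higher grades, but the seriousness qualifiers would then apply to them too. The clinical threshold is for the sponsor to confirm; if a different one is intended, it should be written down.

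The cost is one phrase in Section 6.3. Sample size, schedule and the 3+3 rules are unchanged.

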Any patient who develops a DLT during the "single agent Safety Lead-In" will be removed from additional therapy on this study.

#### 6.1.1.2 Safety Assessment During Cycle 1

An assessment for DLTs will be performed during and at the end of the 21 days of Cycle 1 (Figure 2). In the absence of

DLTs or progressive disease (PD), patients may proceed to a maximum of 12 cycles of combination therapy. After Cycle 2, each subsequent cycle will consist of Hu5F9-G4 (magrolimab) administered on Day 1 of weeks 1 and 3 of the cycle (week 2 will be a week of rest), with dinutuximab administration on Day 2 through 5 of week 1.

The initial dosing of each patient during Cycle 1 safety assessment will be staggered by 7 days for each patient. Three weeks (21 days) must elapse after completion of Cycle 1 in the final patient in the dose finding cohort (Arm A) to allow for safety assessment before treating additional patients at the determined recommended phase 2 dose (RP2D) in Arm B.

The following rules apply to the DLT assessment conducted at the conclusion of Cycle 1 (week 6).

If Dose Level 1 is selected as safe for Cycle 1 based on safety results from the 'Single agent Safety Lead-In', three patients will be enrolled, and the following applies:

- If 0 of the initial 3 patients develops a DLT during Cycle 1, the study will proceed to the expansion cohorts (Arm B) (see Section 6.4).
- If 1 of the initial 3 patients develops a DLT during Cycle 1, then an additional 3 patients will be enrolled at Dose Level 1
  - o If 0 of these 3 additional patients (totaling 1/6) develops a DLT during Cycle 1, the study will proceed to the expansion cohorts (Arm B) (see Section 6.4).
  - If ≥ 1 of these 3 additional patients (totaling ≥ 2/6) develop a DLT during Cycle 1, an additional 3 patients will be enrolled to receive the priming dose followed by Hu5F9-G4 (magrolimab) de-escalated to Dose Level -1 (20 mg/kg) during Cycle 1 (Table 4). The safety of Dose Level -1 will be similarly evaluated in 3-6 patients.
  - If 2 of the initial 3 patients develop a DLT during Cycle 1, an additional 3 patients will be enrolled to receive the priming dose followed by Hu5F9-G4 (magrolimab) de-escalated to Dose Level -1 (20 mg/kg) during Cycle 1. The safety of Dose Level -1 will be similarly evaluated in 3-6 patients.

Table 4: Doses for Hu5F9-G4 (magrolimab) and Dinutuximab during Dose Finding Cohort (Cycle 1)

Dose Level	Dose of (magrolimab)	Hu5F9-G4	Dose of Dinutuximab

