- k. Other single laboratory values out of normal range that have no clinical correlate and resolve to Grade ≤1 or to baseline within 7 days with adequate medical management.
- 1. Tumor flare phenomenon defined as local pain, irritation, or rash localized at sites of known or suspected tumor.
- m. Grade 3 decrease in vision that resolves to grade 1 or better before the next dose dinutuximab will not be considered a DLT and dose will be modified as per Section 7.3.2. Eye disorders such as sluggish light reflex or other visual disturbances that do not cause visual loss will not be considered DLT. Subtotal or total vision loss will be considered a DLT.
- n. Capillary leak syndrome and/or hypotension (grade 3-4) which resolves to ≤Grade 2 or baseline within 8 hours with maximum supportive care.

Management and dose modifications associated with the above adverse events are outlined in Section 7.

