Doses of Hu5F9-G4 (magrolimab) and dinutuximab in the expansion cohorts may be interrupted, delayed or discontinued depending on how well the participant tolerates the treatment. Dosing visits are not skipped, only delayed. Both Hu5F9-G4 (magrolimab) and dinutuximab must be delayed at the same time. Protocol therapy must be discontinued for dose delays greater than 14 days except for reasons outlined in **Section 6.6**. In such cases, the Protocol Principal Investigator must be consulted prior to resuming treatment.

For the expansion cohorts, patients will continue to be monitored for occurrence of DLT during Cycle 1. If 2 of the first 5 patients or if  $\geq$ 2 of 6 patients experience DLT, the Principal Investigator will discuss with all study investigators and with CTEP whether further addition of patients is needed to re-assess the RP2D.

Monitoring of all safety and toxicity data is done by the Principal Investigator and the Corresponding Organization on a real-time basis as data are entered into Medidata Rave using the Web Reporting Module. All participating sites are expected to notify the Principal Investigator when a DLT has occurred.

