## 7 DOSING DELAYS/DOSE MODIFICATIONS

The administration of Hu5F9-G4 (magrolimab) (in the "single agent Safety Lead-In" and/or during cycles of the combination cycles with Hu5F9-G4 (magrolimab) and dinutuximab) will be modified according to the attribution (possibly, probably or definitely related) to either Hu5F9-G4 (magrolimab) or dinutuximab.

The National Cancer Institute (NCI) CTCAE Version 5.0 will be used to grade AEs. Patients enrolled in this study will be evaluated clinically and with standard laboratory tests before and at regular intervals during their participation in this study as specified in this section.

Patients will be evaluated for AEs (all grades), SAEs and AEs requiring study drug interruption or discontinuation at each study visit for the duration of their participation in the study.

The primary approach to mild AEs (Grades 1–2) is supportive and symptomatic care. The general approach to clinically significant and/or unacceptable toxicity (Grade 3 AEs) is holding study treatment until the toxicity resolves (≤ Grade 2) and then resume at one dose level lower, if clinically indicated. Supportive therapy must be administered per standard clinical practice. Consultation with the protocol PI and/or the PED-CITN Coordinating Center is required.

Adverse Event specific guidelines are provided below.

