# 7.1 Dosage modification for Hu5F9-G4 (magrolimab)

Nausea	Management/Next Dose for Hu5F9-G4 (magrolimab)	
≤ Grade 1	No change in dose	
Grade 2	Hold until ≤ Grade 1. Resume at same dose level.	
Grade 3	Hold until < Grade 2. Resume at one dose level lower, if indicated.*	
Grade 4	Off protocol therapy	
*Patients requiring a delay of >2 weeks should go off protocol therapy.		
Recommended managen	nent: antiemetics	

Vomiting	Management/Next Dose for Hu5F9-G4 (magrolimab)	
≤ Grade 1	No change in dose	
Grade 2	Hold until ≤ Grade 1. Resume at same dose level.	
Grade 3	Hold until < Grade 2. Resume at one dose level lower, if indicated.*	
Grade 4	Off protocol therapy	
*Patients requiring a de	lay of >2 weeks should go off protocol therapy.	
Recommended manage	ement: antiemetics	

Diarrhea	Management/Next Dose for Hu5F9-G4 (magrolimab)
≤ Grade 1	No change in dose
Grade 2	Hold until ≤ Grade 1. Resume at same dose level.
Grade 3	Hold until < Grade 2. Resume at one dose level lower, if indicated.*
Grade 4	Off protocol therapy
*Patients requiring	g a delay of >2 weeks should go off protocol therapy.

Recommended management: Loperamide antidiarrheal therapy with dosage schedule: 4 mg at first onset, followed by 2 mg with each loose motion until diarrhea-free for 12 hours (maximum dosage: 16 mg/24 hours)

Adjunct anti-diarrheal therapy is permitted and should be recorded when used.

Neutropenia	Management/Next Dose for Hu5F9-G4 (magrolimab)	
≤ Grade 1	No change in dose	
Grade 2	No change in dose.	
Grade 3	No change in dose.	
Grade 4 Hold until $\leq$ Grade 2. Resume at same dose level.*		
*Patients requiring a de	lay of >2 weeks should go off protocol therapy.	

Thrombocytopenia Management/Next Dose for Hu5F9-G4 (magrolimab)		
≤ Grade 1	de 1 No change in dose	
Grade 2	No change in dose.	
Grade 3 Hold until ≤ Grade 2. Resume at same dose level. *		
Grade 4 Hold until ≤ Grade 2. Resume at one dose level lower, if indicated. *		
*Patients requiring a del	ay of >2 weeks should go off protocol therapy.	

Anemia	Management/Next Dose for Hu5F9-G4 (magrolimab)
≤ Grade 1	No change in dose
Grade 2	No change in dose
Grade 3 hemolytic anemia that is	

Anemia	Management/Next Dose for Hu5F9-G4 (magrolimab)
	First occurrence: Reduce by 1 dose level.  • If recurs after 1 dose level reduction: permanently discontinue unless patient is clinically benefitting.
Grade 4	First occurrence: permanently discontinue unless patient is clinically benefitting.

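### By default Section 6.3 makes isolated Grade 3-4 neutropenia a DLT while excepting neutropenic fever, which does not fit the neutropenia rows of Section 7.1

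*Combined protocol and SAP*

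**What the plan says.** Section 6.3 of the combined protocol and SAP sets a default. Events of Grade 3 or higher that are at least possibly related to a study agent, in the 21-day Safety Lead-In or the 21 days of Cycle 1, "will be considered DLTs with the following additional criteria or exceptions".

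The hematologic list then has three bullets. Anemia is not a DLT, apart from significant Grade 3 hemolytic anemia. A low platelet count without hemorrhage is not a DLT unless it stays below 25,000/mcL for more than 14 days. The third bullet reads, in full, "Grade 3 or 4 lymphopenia or leukopenia not associated with other clinically significant consequences". It has no verb, and neutropenia is not in it.

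Two items under the non-hematological heading come close. Item i excepts febrile cases; it begins "Grade 3 or 4 infection or neutropenic fever although Grade 4 infection uncontrolled". Item k begins "Other single laboratory values out of normal range that have no clinical correlate" and requires resolution to Grade 1 or baseline within 7 days.

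Under Section 6.1.1.1, repeated in Section 6.5.1, a patient with a DLT in the Lead-In "will be removed from additional therapy on this study". Section 7 says that its magrolimab modifications apply in the "Safety Lead-In' and/or during cycles of the combination cycles". The neutropenia table in Section 7.1 gives no dose change at Grade 3. At Grade 4 it says to hold until Grade 2 or less and then "Resume at same dose level"; a delay of more than two weeks ends protocol therapy.

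**The concern.** The DLT count decides whether 30 mg/kg stands or falls to 20 mg/kg, and the recommended phase 2 dose is a primary objective (Section 1.1.2). In the Lead-In it also decides whether a child stays on treatment. An event that literally counts as dose-limiting, while its more serious febrile form does not, looks like an omission rather than a choice.

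The case is foreseeable. Neutrophil count decreased is a listed risk of both agents (Sections 10.1.1.1 and 10.1.1.2). Section 6.3 describes the patients as heavily pretreated, and Section 3.1.7 admits them at a neutrophil count of 1,000/mcL. The definition also reaches Arm B: the first three patients there are assessed for DLT to confirm the dose (Section 6.1.1.2), and in the expansion cohorts "patients will continue to be monitored for occurrence of DLT during Cycle 1" (Section 6.4).

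**Working it through.** **Text.** The provisions side by side, for related neutropenia without fever:

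| Provision | Grade 3 | Grade 4 |
|---|---|---|
| 6.3 default rule | DLT | DLT |
| 6.3 hematologic list | not named | not named |
| 6.3 item i | covers neutropenic fever only | covers neutropenic fever only |
| 6.3 item k | exempt if resolved to Grade 1 or baseline in 7 days, if the item reaches hematologic values | same |
| 6.1.1.1 and 6.5.1 (Lead-In) | off therapy if a DLT | off therapy if a DLT |
| 7.1 | no dose change | hold to Grade 2 or less, then same dose |

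Leukopenia in the third bullet does not clearly include neutropenia. Both agents' adverse event lists carry neutrophil count decreased and white blood cell decreased as separate terms, and Section 7.1 gives neutropenia its own table. Of the three hematologic tables in Section 7.1 (neutropenia, thrombocytopenia, anemia), only neutropenia has no matching rule in Section 6.3.

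**Size.** The plan states no operating characteristics for its DLT rule, so there is no figure to reproduce. The calculation needs:

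- The 3+3 rule in Section 6.1.1: a window is passed with 0 of 3 DLTs, or with 1 of 3 followed by 0 of 3 more.
- q, the rate of all other DLTs per window. Assumed at 5%, 10% or 15%; not in the documents.
- n, the rate of isolated related Grade 3-4 neutropenia per window. Assumed at 5% to 30%; not in the documents. The two kinds of event are taken as independent.

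If isolated neutropenia counts, the DLT rate per window is p = 1 - (1 - q)(1 - n). If it is exempt, p = q. The chance of passing one window is (1 - p)^3 + 3p(1 - p)^2 × (1 - p)^3 = (1 - p)^3 + 3p(1 - p)^5.

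For q = 10%:

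- exempt, p = 0.100: 0.729 + 0.177 = 0.906
- n = 5%, p = 0.145: 0.625 + 0.199 = 0.824
- n = 10%, p = 0.190: 0.531 + 0.199 = 0.730
- n = 20%, p = 0.280: 0.373 + 0.163 = 0.536
- n = 30%, p = 0.370: 0.250 + 0.110 = 0.360

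Chance of passing one window for all assumed rates:

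| Other DLTs | Exempt | n = 5% | n = 10% | n = 20% | n = 30% |
|---|---|---|---|---|---|
| 5% | 0.973 | 0.910 | 0.824 | 0.622 | 0.425 |
| 10% | 0.906 | 0.824 | 0.730 | 0.536 | 0.360 |
| 15% | 0.814 | 0.725 | 0.632 | 0.454 | 0.301 |

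**The case against.** The strongest reply is that Section 6.3 is strict, not silent: an unexcepted Grade 3 event is a DLT, and that is a written rule. This is right as far as it goes. What it leaves unexplained is why neutropenia with fever escapes the rule and neutropenia without fever does not.

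A second reply is that item k already exempts brief episodes. Item i sits under the same non-hematological heading and plainly deals with a neutrophil event, so the heading may not be a firm boundary. That stands in part. If item k applies, only episodes lasting beyond 7 days remain open. Its reach is nevertheless unclear, and its test is stricter than the Grade 2 and two-week limits of Section 7.1.

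A reader might infer that a site cannot obey both sections, or that the Section 7.1 rows prove neutropenia was never meant to be dose-limiting. The documents support neither. The Lead-In removal rule is specific and can be read to override Section 7.1. Significant Grade 3 hemolytic anemia is expressly a DLT and yet has a dose-reduction row in Section 7.1, so a row there does not settle DLT status.

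Weekly review of the study chair's DLT evaluations (Section 13.1.2) would probably lead to one reading being applied. If it departs from the literal rule, it would be chosen after the event is known.

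The probabilities also assume that every event is detected. The Arm B calendar marks no blood count in Weeks 3-4 of Cycle 1, so laboratory-only events could be missed there.

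**Conclusion.** The point stands as an incoherent DLT classification that should be corrected. Literally applied, afebrile Grade 3 neutropenia ends a Lead-In patient's treatment and counts toward de-escalation, while the febrile form does not count and Section 7.1 calls for no dose change.

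The size is illustrative. With other DLTs at an assumed 10%, the chance of passing one window is 0.91 with neutropenia exempt, and between 0.82 and 0.36 when it counts at 5% to 30%. All these rates are assumptions.

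Two further inferences should be avoided. A reader might take the 20% upper bound of the less-likely category in the adverse event lists as a ceiling, but Section 7.3 puts neutropenia among dinutuximab reactions at 25% or more, and neither source states a grade. A reader might also square the one-window figures to cover the Lead-In and Cycle 1 together. That needs the same rate in both windows, which the documents do not support: the Lead-In is magrolimab alone, and the most common related events listed for that drug in Section 2.1.6, down to 11.0%, do not include neutropenia.

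**What to change.** Change Section 6.3 only, under Hematologic Toxicity. End the lymphopenia/leukopenia bullet with *will not be considered a DLT*, and add: *Grade 3 neutropenia will not be considered a DLT. Grade 4 neutropenia will not be considered a DLT unless it fails to recover to Grade 2 or less within 14 days despite supportive care.* This follows the Section 7.1 neutropenia rows, their two-week limit, and the 14-day platelet rule already in Section 6.3.

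If the sponsor does intend isolated neutropenia to be dose-limiting, Section 6.3 should say so, and the Section 7.1 rows should be aligned for the Lead-In and Cycle 1.

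The cost is one completed bullet and two sentences in an amendment, with no added patients. Grade 4 cases need repeat counts until recovery, and a late onset could run past day 21. The platelet rule and the Section 7.1 hold already imply such follow-up. No new rule on G-CSF is needed: Section 3.1.7 concerns eligibility and Section 3.2.10 the start of treatment, so restricting its use during therapy would be a separate policy.
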